8.1 Definition of Protocol Deviations and Analysis Sets

Important protocol deviations (IPDs) are protocol deviations that might significantly affect the completeness, accuracy, and/or reliability of the study data or that might significantly affect a subject's rights, safety, or well-being.

IPDs include:

- Subjects that are dosed on the study despite not satisfying the inclusion criteria;
- Subjects that develop withdrawal criteria whilst on the study but are not withdrawn;
- Subjects that receive the wrong treatment or an incorrect dose;
- Deviation from Good Clinical Practice (GCP)
- Missed safety assessments

IPDs are clinically important if they lead to the exclusion of a subject from an analysis set, or if they could impact the key objectives of the study (see Section 10.2).

A list of IPDs can be found in Appendix 18.1, including possible consequences for assignment to analysis sets; clinically important protocol deviations (cIPDs) are highlighted accordingly. The final assessment of whether these protocol deviations lead to exclusion from an analysis population will be made at the DRM.

8.2 Definition of Analysis Sets and Subgroups

For purposes of analysis, the following populations are defined in Table 1.

Table 1 Analysis Sets

Population	Description
Screening	All participants who sign informed consent
Dose Escalation	All subjects treated in dose escalation cohorts who did not miss >4 cumulative days planned doses of M8891 in the first cycle of the dose escalation part for other than safety reasons
Safety	The Safety Analysis Set will include all subjects who receive at least one dose of trial treatment.
Pharmacokinetic CCI	All subjects from the safety analysis set without major protocol deviations/violations or events that would affect PK. Subjects in the PK analysis set must have received at least 1 dose of M8891 and have sufficient M8891 plasma concentration data to enable the calculation of at least one PK parameter. Sufficient concentration data is defined as at least 3 valid, post-dose concentration points in the PK profile to obtain any PK parameter.
CCI	

PK Pharmacokinetic; WBC White blood cell.

9 General Specifications for Data Analyses

All tables and listings (and titles and footnotes for figures) will be produced using the Courier New font with a font size of 10 points. A font size of 9 points will be acceptable in cases where a font size of 10 points does not fit.

All TLFs will be produced using a paper size of US letter in landscape with 1 inch margins on all four sides.

Significance level:

There is no formal significance level for this trial and all analyses are considered descriptive. If confidence intervals or credibility intervals are mentioned, the level will be 95% unless otherwise specified.

Cutoff

For the analysis after the end of dose escalation for monotherapy, the cutoff will be 22 days after the first treatment day of the last subject enrolled into the monotherapy dose escalation cohort.

Pooling of centers:

Because of the anticipated small number of subjects enrolled in each center data will be pooled across centers, and the factor center will not be considered in statistical models or for subgroup analyses.

Definition of baseline:

In general, the last non-missing measurement prior to first trial drug administration will be used as the baseline measurement, unless otherwise specified (e.g. Section 15.7).

Definition of duration:

Duration in days will be calculated by the difference of start and stop date + 1 day (e.g. survival time (days) = date of death – date of first treatment + 1).

In case smaller units are of interest, duration will be calculated as stop date and time – start date and time.

The time since an event (e.g. time since first diagnosis) will be calculated as reference date minus date of event.

Conversion factors:

The following conversion factors will be used to convert days into months or years: 1 month = 30.4375 days, 1 year = 365.25 days.

Handling of missing data:

Unless otherwise specified (e.g. Section 11.3, 15, 16.1), missing data will not be replaced.

In all listings imputed information will be flagged accordingly.

Days in Trial and on Treatment:

The first study day is the day of informed consent. The first treatment day is the day of first administration of Investigational Medicinal Product (IMP). The day before the first treatment/study day will be labelled as study/treatment day -1; there will be no study/treatment day 0.

9.1 Listings

All original and derived parameters relevant to the study endpoints as well as demographic and disposition data will be listed, including repeated and unscheduled measurements.

All dates and times will be presented in the format 'DDMMMYYYY' and 'HH:MM', respectively. Data will be listed with the same number of decimal places as in the original data.

Subjects will be identified in listings by their Subject ID.

9.2 Tables

Presentation of continuous and categorical variables

The following summary statistics will be used to summarize the trial data (other than PK concentration and PK parameters) per dose group (as defined by both dosing level and frequency) unless otherwise specified:

- Continuous variables: number of non-missing observations, number of missing observations, arithmetic mean (Mean), standard deviation (Sd), median (Median), minimum (Min), and maximum (Max) (in case less than 5 individual values are present: only mean, min and max will be given)
- Categorical variables: frequencies and percentages.

The following conventions are applied for reporting descriptive statistics of all continuous data (n refers to the number of decimal places reported for the original data):

Mean, Median n decimal digits

Sd n+1 decimal digits

Min, Max n decimal digits

Confidence Intervals (CIs) n decimal digits

Credibility Intervals n decimal digits

Unless otherwise stated, the calculation of proportions will be based on the number of subjects in the analysis set of interest. Therefore, counts of missing observations will be included in the denominator and presented as a separate category.

In case the analysis refers only to certain cycles and/or visits, percentages will be based on the number of subjects still present in the trial at that cycle and/or visit, unless otherwise specified.

All tables will be sorted by scheduled time point in chronological order, unless otherwise specified.

Unscheduled measurement will not be used for summary tables or statistical analysis, unless it was a repeated measurement, performed due to technical reason or unreliable values for a planned assessment.

Should a repeated measurement occur prior to IMP administration, the last obtained reliable value prior to dosing will be used as baseline, unless otherwise specified.

Should a repeated measurement occur after IMP administration, then the measurement closest to the scheduled time will be used in the descriptive statistics and for changes from baseline. In case this rule does not identify a unique measurement to use, the earliest one among those identified will be used. Again, this rule should be used unless otherwise specified (see e.g. Section 15.7).

Presentation of PK concentration data

M8891 concentration data will be descriptively summarized using: number of non-missing observations (N), arithmetic mean (Mean), standard deviation (Sd), coefficient of variation (CV%), minimum (Min), median (Median) and maximum (Max). If there are fewer than 3 observations, only N, Min, and Max will be reported.

Descriptive statistics of PK concentration data will be calculated using values with the same precision as the source data, and rounded for reporting purposes only. The following conventions will be applied when reporting descriptive statistics of PK concentration data:

Mean, Min, Median, Max: 3 significant digits
Sd: 4 significant digits
CV%: 1 decimal place

Presentation of PK parameter data

Pharmacokinetic parameter data will be descriptively summarized using: number of non-missing observations (N), arithmetic mean (Mean), standard deviation (Sd), coefficient of variation (CV%), minimum (Min), median (Median), maximum (Max), geometric mean (GeoMean), the geometric coefficient of variation (GeoCV%) and the 95% confidence interval for the GeoMean (LCI 95% GM, UCI 95% GM). For time to reach maximum observed concentration (t_{max}), only N, Min, Median and Max will be reported.

The PK parameter maximum observed plasma concentration (C_{max}) will be reported with the same precision as the source data and t_{max} will be reported to 2 decimal places. All other PK parameters will be reported to 3 significant figures. In export datasets, as well as in the Study Data Tabulation Model (SDTM) PP domain, PK parameters will be provided with full precision, and will not be rounded. Descriptive statistics of PK parameter data will be calculated using full precision values, and rounded for reporting purposes only.

The following conventions will be applied when reporting descriptive statistics of PK parameter data:

Mean, Min, Median, Max, GeoMean, 95% CI: 3 significant digits Sd: 4 significant digits CV%, GeoCV%: 1 decimal place

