15.7 ECG

All analysis of electrocardiogram (ECG) data will be based on the safety population.

Triplicate values will be handled as follows: listings will contain the individual triplicates and the aggregated results. Summaries will only use the aggregated values. The aggregation of triplicate ECGs will be performed using the arithmetic mean for all parameters at each time point. The aggregated values of the last triplicate ECG measurement prior to first trial drug administration will be used as the baseline measurement.

Results will be listed, including the following information:

- Time point
- Time of measurement
- Position
- Heart rate (beats/min)
- PQ/PR duration (ms)
- RR duration (ms)
- QRS duration (ms)
- QT corrected using Fridericia's formula: QTcF = QT/ $\sqrt[3]{RR}$ (ms)
- Rhythm evaluation
- Whether ECG is abnormal
- Clinical significance if ECG is abnormal

Potentially clinically significant abnormal values of ECG will be flagged according to the following criteria:

Parameter	Potentially Clinically Significant Abnormalities (PCSA) Criteria
Heart rate	≤ 50 bpm and decrease from baseline ≥ 20 bpm ≥ 120 bpm and increase from baseline ≥ 20 bpm
PQ/PR	≥ 220 ms and increase from baseline ≥ 20 ms
QRS	≥ 120 ms
QTcF absolute	Prolonged: >450 ms (Male), >470 ms (Female) Potentially significant abnormality: ≥ 500 ms
QTcF change from baseline	Prolonged: Increase from baseline > 60 ms

Only the aggregated measurement will be flagged as described. The flagging of the aggregated measurement will be performed by applying the above rules directly on the averaged ECG parameters.

For display of overall assessment of the result of the ECG as normal, abnormal not clinically significant, and abnormal clinically significant, the worst result of the triplicates will be considered for the analysis of the aggregated measurements.

The ECG parameters will be summarized by descriptive statistics per time point including absolute values and change from baseline. Number and percentages for subjects meeting the PCSA Criteria will also be provided. For the investigator's overall ECG assessment, a shift table from baseline to the worst on-treatment result will be created.

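### SAP 9.2's rule for repeated post-dose measurements has no reliability condition, so a recorded unreliable value is usually summarised instead of its valid repeat

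*SAP*

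**What the plan says.** Four statements in SAP 9.2 (Tables) bear on this.

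- **Admission.** Unscheduled values stay out of summaries and analyses "unless it was a repeated measurement, performed due to technical reason or unreliable values for a planned assessment".
- **Before dosing.** "Should a repeated measurement occur prior to IMP administration, the last obtained reliable value prior to dosing will be used as baseline, unless otherwise specified".
- **After dosing.** "Should a repeated measurement occur after IMP administration, then the measurement closest to the scheduled time will be used in the descriptive statistics"; the sentence goes on to cover changes from baseline.
- **Ties and exceptions.** "In case this rule does not identify a unique measurement to use, the earliest one among those identified will be used". The closing sentence allows for exceptions and names the ECG section as an example: "Again, this rule should be used unless otherwise specified (see e.g. Section 15.7".

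SAP 15.7 (ECG) says of triplicates: "The aggregation of triplicate ECGs will be performed using the arithmetic mean for all parameters at each time point". It also gives an ECG baseline rule. Neither it nor SAP 15.4 (laboratory) or 15.5 (vital signs) says what to do with an unreliable post-dose value. SAP 9.1 requires repeated and unscheduled values to be listed.

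**The concern.** The admission rule and the post-dose selection rule work against each other. A repeat is let in because something was wrong with the planned measurement. The choice between the two is then made on distance from schedule alone, and that criterion favours the earlier value, as does the tie-break. A programmer following the text would summarise the value known to be bad and leave out its replacement. The baseline sentence shows that the SAP already has the notion of a reliable value and simply does not carry it into the next rule.

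At stake are the by-dose, by-time-point descriptive statistics and changes from baseline for laboratory and vital-sign data, which are Part 1 secondary safety endpoints. Cohorts start at 3 subjects. With fewer than 5 values SAP 9.2 reports only mean, minimum and maximum, so the median, which would resist a single bad value, is not shown.

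**Working it through.** The plan gives no figure to reproduce. The check applies the rule as written.

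**Inputs**
- Selection rule and tie-break: SAP 9.2.
- Part 1 visit windows: protocol Table 1, ±1 day for Cycle 1 Days 8 and 15, ±2 days for visits from Cycle 2 on.
- Cohort size 3: protocol 5.1.3.1. Larger dose levels of 6 and 9: protocol 8.1.1.
- Assumed, because the documents do not give them: the delay to the repeat, and that the original is equally likely to fall on each day of its window.

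**Formula.** Let *o* be the original's offset from schedule (negative = early) and *g* > 0 the delay to the repeat. The original is selected if |*o*| ≤ |*o* + *g*|, which is the same as *o* ≥ −*g*/2. The repeat wins only if the original was early by more than half the delay.

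**Original on or after schedule.** Then *o* ≥ 0, the condition always holds, and the original is used in 100% of cases. If timing is compared by day and the repeat is on the same day, the two tie and the original is again used.

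**±1 day window (*o* = −1, 0, 1)**
- *g* = 1: the repeat wins only at *o* = −1 (distance 0 against 1). Original used in 2/3 = 67%.
- *g* = 2: at *o* = −1 the distances tie at 1, and the earliest is taken. Original used in 3/3 = 100%.

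**±2 day window (*o* = −2, …, 2)**
- *g* = 1: the repeat wins at *o* = −2 and −1. Original used in 3/5 = 60%.
- *g* = 2: the repeat wins at *o* = −2; *o* = −1 ties. Original used in 4/5 = 80%.
- *g* = 3: the repeat wins at *o* = −2 only (distance 1 against 2). Original used in 4/5 = 80%.

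**Direction without the uniform assumption.** For any timing symmetric about the schedule, *o* ≥ 0 has probability at least one half and lies inside *o* ≥ −*g*/2, so the original is used at least half the time.

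**Effect on a table.** An error *e* in one subject's analysed value shifts the mean of *n* subjects by *e*/*n*. For ECG, the triplicate average comes first, so one tracing wrong by 60 ms (an illustrative size) moves that subject's value by 60/3 = 20 ms and the group mean by 20/*n*:

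| Subjects in dose group | One tracing wrong by 60 ms | Whole triplicate average wrong by 60 ms |
|---|---|---|
| 3 | 20/3 = 6.7 ms | 60/3 = 20 ms |
| 6 | 20/6 = 3.3 ms | 60/6 = 10 ms |
| 9 | 20/9 = 2.2 ms | 60/9 = 6.7 ms |

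**After the fix.** With a reliability condition, a value judged unreliable is selected in 0% of cases.

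**The case against.** The best reply is that the intent is plain. Repeats are admitted because planned values failed, and the baseline sentence takes the reliable value, so the time rule was probably meant to choose among usable values. The SAP also provides for a data review meeting before database lock (Section 6), where known-bad values could be dealt with. All of this is plausible, but neither the rule nor the description of that meeting says so, and the text as it stands gives the opposite result.

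Several stronger readings are tempting and are not supported:

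- **That the valid repeat is lost.** SAP 9.1 keeps it in the listings. It is missing only from descriptive statistics and changes from baseline.
- **That every repeat is mishandled.** If a technical failure left no value, the repeat is the only measurement and the rule works.
- **That the default rule governs ECG, so that a 60 ms artefact moves a 3-subject mean by 20 ms.** ECG is the domain named as a possible exception. Section 15.7 averages triplicates, so a single faulty tracing gives about 7 ms; 20 ms needs the whole average to be wrong. How a repeated ECG set is handled is left open, so no share of wrongly chosen ECG values is claimed here.
- **That dose-finding is compromised.** The DLT analysis (SAP 15.1) does not use this rule, and SMC outputs are in a separate plan (SAP Section 4). The general summary conventions in 9.2 exclude PK concentrations and parameters.

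It is also fair that 3 is the smallest group. Protocol 8.1.1 foresees dose levels of 6 and 9 and requires at least 6 subjects at the MTD or RP2D, where one bad value weighs less. The SAP further states: "There is no formal significance level for this trial and all analyses are considered descriptive". The harm is therefore a wrong summary value, not a wrong test.

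**Conclusion.** The rule is wrong as written, and worth correcting. Where an unreliable post-dose value was recorded and then repeated, SAP 9.2 usually summarises the unreliable one: always if it was taken on or after its scheduled time, and in 67% or 60% of one-day-later repeats for windows of ±1 and ±2 days. Those two percentages rest on uniform timing within the window and an assumed delay; the direction needs only timing that is symmetric about the schedule.

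The consequence is limited to descriptive summaries and changes from baseline, mainly laboratory and vital signs, and is largest in the smallest dose groups. For ECG the gap is different: Section 15.7 lacks a rule for an unreliable post-dose set. How many table entries would change cannot be stated, because the number of repeats is not given.

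**What to change.** Replace the post-dose selection sentences in SAP 9.2 with wording such as:

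> Where a planned post-dose measurement has been repeated, summaries and changes from baseline use the reliable measurement nearest to its scheduled time (the earliest if two are equally near). Values judged unreliable are listed and flagged but not summarised.

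Add to SAP 15.7 that the same rule is applied to ECG tracings before the triplicate is averaged.

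The cost is a few lines of SAP text and a reliability flag in the derivation programs. The baseline rule already needs that judgement, and the data review meeting is a natural place to confirm it. No new data are required.

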9.3 Software

Pharmacokinetic parameters will be derived using PPD Version 6.4 or higher. All other statistical analyses will be performed using PPD version 9.3 or higher or R and

packages PPD or higher, or East version 6.4 or higher. PK figures and tables may be prepared using PPD version 9.3 or higher.

Trial Subjects

The subsections in this section include specifications for reporting subject disposition and treatment/trial discontinuations. Additionally, procedures for reporting protocol deviations are provided.

10.1 Disposition of Subjects and Discontinuations

Subject disposition will be presented using the screening population and will be summarized (n and percentages) by dose group (including dosing frequency) and overall. Subject disposition will also be summarized by site. The following information will be included:

- Total number of subjects screened (i.e. subjects who gave informed consent)
- Number of subjects who discontinued from trial prior to treatment, overall and grouped by main reason (e.g. the failed specific inclusion or exclusion criteria, withdraw of consent)
- Number of treated subjects
- Number of subjects that discontinued the treatment, overall and grouped by main reason
 - o For the first cycle (frequencies calculated using number of subjects treated):
 - Number of subjects treated in the cycle
 - Number of subjects that discontinued the treatment, overall and grouped by main reason
 - Number of subjects who completed the cycle
 - o For cycles after the first:
 - Number of subjects treated in the cycle who completed the previous cycle (denominator for frequency is the number of subjects who completed the previous cycle)
 - Number of subjects that did not continue treatment in the cycle (but were treated in the previous cycle), overall and grouped by main reason (denominator for frequency is the number of subjects who completed the previous cycle)
 - Number of subjects that discontinued the treatment during the cycle after first dose, overall and grouped by main reason (denominator for frequency is the number of subjects treated in cycle)
 - Number of subjects who completed the cycle (denominator for frequency is the number of subjects treated in cycle)
- Number of treated subjects who terminated the study, overall and grouped by main reason

The percentages for subjects treated will be based on the number of subjects in the safety population for each treatment sequence and on the number of screened subjects in the overall group.

In the corresponding individual listing date of informed consent, protocol version, first and last date of dosing and study termination date will be presented, as well as primary reason for study and treatment discontinuation.

The listing of screening failures will include the following information:

- Date of informed consent
- Protocol version
- Date of screening failure
- Reason for non-inclusion:
 - Subject did not meet all eligibility criteria (as specified in ClinBase, including the description of the violated criteria)
 - Subject withdrew informed consent
 - o Other reasons (specified in ClinBase)

The disposition listings will be sorted by dose group and subject ID.

10.2 Protocol Deviations

10.2.1 Important Protocol Deviations

The following summary tables and listings of IPDs will be provided (separately for pre-/post inclusion deviations), based on the safety population:

- Frequency table of IPDs by classification and description
- Listing of IPDs (sorted by dose group and subject ID), indicating whether it was a cIPD

The frequency table will be by dose group and overall.

10.2.2 Reasons Leading to the Exclusion from an Analysis Set

The exclusion of subjects from analysis populations, e.g. due to clinically important protocol deviations, will be summarized by counts and frequencies for all occurring reasons of exclusion for each analysis population.

Exclusions will also be listed, including:

- Population that the subject is excluded from
- Reason of exclusion

11 Demographics and Other Baseline Characteristics

11.1 Demographics

Demographic characteristics will be listed (sorted by dose group and subject ID) and summarized by dose group and overall, based on the safety population, showing the following:

- Demographic characteristics
 - Gender: male, female
 - Race: White, Black or African American, Asian, Native Hawaiian or other Pacific Islander, American Indian or Alaska Native, Other
 - Ethnicity: Hispanic or Latino, Not Hispanic or Latino
 - Age (years), calculated as (date of informed consent date of birth + 1) / 365.25
 - Age categories: $<65, 65-74, 75-84, \ge 85$ years
 - Weight (kg)
 - Height (cm)
 - Body Mass Index (BMI), calculated as (weight in kg) / (height in meters)² (kg/m²)
- Center

